8.2.3.4. Risk assessment

[figure not shown]
[Figure 5](#) illustrates the probability of not meeting holding rule 1 and 2 for 16 active vaccine recipients at the first planned IDMC meeting.

CONFIDENTIAL

209544 (RSV MAT-004)
Protocol Amendment 3 Final

Figure 5 Evaluations based on 16 active recipients - Risk assessment curve for one formulation based on the proposed safety holding rules across active groups

Safety holding rule after 16 subjects in active vaccine groups enrollment

Thus, with 16 active vaccine recipients across study groups:

- Each holding rule 1a-1c has a more than 90% chance of not being met for vaccination with a true incidence rate below 1% and has a more than 80% chance of being met for vaccination with a true incidence rate above 10%.
- Each holding rule 2a-2c has a more than 90% chance of not being met for vaccination with a true incidence rate below 10% and a more than 80% chance of being met for vaccination with a true incidence rate above 35%.

The risk of ERD related to boosting pre-existing maternal antibody and transfer of vaccine-induced neutralizing antibodies from mother to infant, is considered negligible. However, as data evaluating this risk are expected before the vaccination of larger numbers of pregnant women, surveillance and evaluation of all RTIs in infants and medically attended-RTIs in mothers (Section 8.4) has been implemented.

To assess the ability of the study to demonstrate with 90% power that the progression rate from RSV infection to severe disease or hospitalization is lower than the 80% rate seen in the historical formalin-inactivated vaccine, the accrual of at least 5 cases of RSV infection among infants will be needed. With a one-sided 5% type one error rate and assumption of a 10% rate of infection progressing to severe disease or hospitalization, 5 infections can provide at least 90% statistical power to demonstrate the progression rate from RSV infection to severe disease or hospitalization is less than 80%.

Table 20 shows examples of the rate of progression to more severe disease or hospitalization and their corresponding upper 95% confidence intervals when 5 or 10 cases of RSV among infants are accrued. Where the upper limit of the 95% confidence interval is above 80%, this suggests a rate of severe disease that is equivalent to the historical formalin-inactivated vaccine. Where the upper limit is less than 80%, this would suggest that the current vaccine is not equivalent to the historical vaccine in terms of progression to more severe RSV disease.

CONFIDENTIAL209544 (RSV MAT-004)
Protocol Amendment 3 Final**Table 20** Rates of progression to more severe RSV disease or RSV associated hospitalization

| Observed number of infected infant subjects | Observed Number of hospitalizations or severe disease | Rate of hospitalization or severe disease | |
|---|---|---|--------------|
| | | Actual | Upper 95% CI |
| 5 | 1 | 20% | 71.6% |
| 5 | 2 | 40% | 85.3% |
| 10 | 1 | 10% | 45% |
| 10 | 2 | 20% | 56% |
| 10 | 3 | 30% | 65.2% |
| 10 | 4 | 40% | 73.8% |
| 10 | 5 | 50% | 81.3% |

8.3. Adverse Events (AEs), Serious Adverse Events (SAEs) and other events of interest**8.3.1. Time period and frequency for collecting AE, SAE and other safety information**

[Table 21](#) provides an overview of the protocol-required reporting periods for safety (as well as RTI) information.

CONFIDENTIAL

209544 (RSV MAT-004)
Protocol Amendment 3 Final

Table 21 Timeframes for collecting and reporting safety (and RTI) information

| Timepoint | | Before Delivery* | | | | | Delivery / Birth | Post-Delivery* | | | | | |
|-------------------------|--|------------------|----|----|----|-----|------------------|----------------|-------|-------|-------|-----------|-------|
| | | D-28 | D1 | D7 | D8 | D31 | D61 | D 43 | D121 | D181 | D271 | 12 months | |
| Maternal subject visits | | Pre-** | V1 | V2 | V3 | V4 | V5 | V6 | V7 | V8 | | | |
| Infant visits | | | | | | | | V1-NB | V2-NB | V3-NB | V4-NB | C1-NB | V5-NB |
| Event | Administration site and systemic solicited events | | M | | | | | | | | | | |
| | Unsolicited AEs | | M | | | | | | | | | | |
| | Subsequent Pregnancies*** | | | | | | | M | | | | | |
| | AEs/SAEs leading to Withdrawal from the study | | M | | | | | M | | | I | | |
| | SAEs and MAEs | | M | | | | | M | | | I | | |
| | AESIs**** | | M | | | | | M | | | I | | |
| | Medically attended RTI RTI/LRTI | | M | | | | | M | | | I | | |
| | SAEs related to study participation or concurrent GSK medication or vaccine | | M | | | | | | | | | | |

* Approximately monthly contacts pre- and post-delivery also occur within the timeframes described above and are described in Section 1.3. **i.e. consent obtained. Pre = pre-vaccination; V=visit; C = contact; D= Day. *** if subsequent pregnancy occurs during the study, follow-up extends up to 8 weeks post birth of the infant If subsequent pregnancy occurs after Visit 8, report adverse pregnancy outcomes / other SAEs experienced by mother / infant, if known. ****AESIs include adverse pregnancy outcomes, pregnancy related AEs of special interest and neonatal AEs of special interest. Neonatal AEs of special interest identified after V2-NB (e.g., congenital anomalies) will continue to be reported as such

CONFIDENTIAL209544 (RSV MAT-004)
Protocol Amendment 3 Final

The investigator or designee will record and immediately report all SAEs (including RTIs associated with hospitalization of a maternal or infant subject and all adverse pregnancy outcomes), as well as all pregnancy related AESIs and neonatal AESIs to the sponsor or designee via the Expedited AE Reporting Form. This reporting should under no circumstances occur later than 24 hours after the investigator becomes aware of the event, as indicated in Section 10.3.10. The investigator will submit any updated data to the sponsor within 24 hours of it being available.

A post-study AE/SAE is defined as any event that occurs outside of the AE/SAE reporting periods defined in Table 21. Investigators are not obligated to actively seek AEs or SAEs in former study subjects. However, if the investigator learns of any SAE, including a death, at any time after a subject has been discharged from the study, and he/she considers the event to be reasonably related to the study vaccine(s)/product(s), the investigator will promptly notify the Study Contact for Reporting SAEs mentioned in Table 23.

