8.2.3.2. Outcomes of safety evaluations

Safety evaluations will include those performed by investigators, by a blinded safety review team (SRT) composed of GSK RSV team members, and by an unblinded, independent data monitoring committee external to GSK (IDMC). **Details** regarding SRT and IDMC safety evaluations **are provided in a separate IDMC charter.**

- If no safety signal is observed after the first 30 maternal subjects have been enrolled and dosed, this will be documented. GSK will provide investigators with written authorization to enroll and dose the remaining ~ 270 maternal subjects.
- If the IDMC's decision(s) after a safety evaluation require(s) them to take some action (e.g., to suspend, modify, or continue the conduct of the study for all groups or for selected groups), the IDMC Chair (or his/her representative) will notify the study CRDL. The study CRDL will be accountable for notifying investigators in writing of the IDMC's decision(s).

CONFIDENTIAL209544 (RSV MAT-004)
Protocol Amendment 3 Final**8.2.3.3. Study holding rules****8.2.3.3.1. Holding rules assessed by the investigator**

The investigator and /or designees will assess on an ongoing basis whether any of the holding rules in [Table 17](#) have been met, irrespective of the number of subjects enrolled and/or timing of the event relative to dosing.

Table 17 Holding rules assessed by the investigator

| Holding Rule | Event | Number of mothers/infants |
|--------------|--|---------------------------|
| 1a | Maternal death or any life-threatening SAE , or fetal death or unexplained neonatal/infant death up to 1 year of age | ≥ 1 |
| 1b | Any non-life-threatening SAE that cannot be reasonably attributed to a cause other than vaccination (applies to both maternal subjects and infants of vaccinated mothers). | ≥ 1 |
| 1c | Any withdrawal from the study (by the investigator or subject request) following a Grade 3 AE that cannot reasonably be attributed to a cause other than vaccination. | ≥ 1 |
| 1d | Any solicited administration site or systemic event leading to hospitalization , or fever > 40°C (104°F) (oral route) or necrosis at the injection site, within the 7-days (Day 1-7) post-vaccination period. | ≥ 1 |

If the investigator becomes aware of a holding rule (e.g., 1a-1d in [Table 17](#)) being met, he/she will suspend enrolment and study vaccine/product administration and inform GSK as soon as possible (no later than within 24 hours).

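### With 16 active recipients and a one-event trigger, holding rules 1a-1c have an 85.1% chance of not being met at a 1% true rate, not more than 90%

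*Protocol*

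**What the plan says.** Section 8.2.3.4 of the protocol introduces Figure 5, which "illustrates the probability of not meeting holding rule 1 and 2 for 16 active vaccine recipients at the first planned IDMC meeting". The figure carries the label "Safety holding rule after 16 subjects in active vaccine groups enrollment". The text then interprets the curve, opening with "Thus, with 16 active vaccine recipients across study groups", and gives four bounds.

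- Rules 1a-1c, low rate: "Each holding rule 1a-1c has a more than 90% chance of not being met for vaccination with a true incidence rate below 1" per cent.
- Rules 1a-1c, high rate: more than 80% chance of being met above 10%.
- Rules 2a-2c, low rate: more than 90% chance of not being met below 10%.
- Rules 2a-2c, high rate: more than 80% chance of being met above 35%.

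The triggers are set elsewhere. Table 17 in Section 8.2.3.3.1 gives a count of at least one for each of the three rules:

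- 1a covers maternal death, life-threatening SAE, fetal death and "unexplained neonatal/infant death up to 1 year of age | ≥ 1".
- 1b covers "Any non-life-threatening SAE that cannot be reasonably attributed to a cause other than vaccination", in mothers and in "infants of vaccinated mothers). | ≥ 1".
- 1c covers withdrawal "following a Grade 3 AE that cannot reasonably be attributed to a cause other than vaccination. | ≥ 1".

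Table 18 in Section 8.2.3.3.2 requires at least 4 subjects and at least 25% across the active groups for rules 2a-2c.

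**The concern.** A rule that fires on a single event among 16 people is sensitive even to rare events. At a 1% rate the expected number of events among 16 is 0.16, so a chance of no event above 90% looked too high.

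The sentence is the protocol's own description of how often a rule would stop the trial when the true event rate is low. Meeting a rule 1 criterion suspends enrolment and dosing, blocks the randomisation system and requires regulators to be informed. An ethics committee, the IDMC or a regulator reading this sentence would take the chance of that happening to be under 10% per rule for any true rate below 1%.

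**Working it through.** **Inputs**

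- Number at risk: n = 16 active recipients (Section 8.2.3.4).
- Trigger for each of rules 1a, 1b and 1c: at least 1 event (Table 17).
- Trigger for each of rules 2a-2c: at least 4 subjects and at least 25% (Table 18). With n = 16, 25% is 4, so the two conditions coincide.

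**Model.** The number of recipients with an event is binomial, X ~ Bin(16, p).

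- Rule 1 not met: P(X = 0) = (1 − p)^16.
- Rule 2 not met: P(X ≤ 3).

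**The three bounds that reproduce**

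| Statement in Section 8.2.3.4 | Calculation | Result |
|---|---|---|
| Rule 1 met, rate above 10%: more than 80% | 1 − 0.90^16 | 81.5% |
| Rule 2 not met, rate below 10%: more than 90% | P(X ≤ 3), p = 0.10 | 93.2% |
| Rule 2 met, rate above 35%: more than 80% | P(X ≥ 4), p = 0.35 | 86.6% |

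Each of these holds at the named rate itself, so this is evidently the model behind the section, and the named rate is meant as the limit of the range over which the bound applies.

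**The bound that does not.** Rule 1 not met, rate below 1%, stated as more than 90%:

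| True rate p | (1 − p)^16: not met | Met |
|---|---|---|
| 0.50% | 92.3% | 7.7% |
| 0.65% | 90.1% | 9.9% |
| 0.70% | 89.4% | 10.6% |
| 0.80% | 87.9% | 12.1% |
| 0.90% | 86.5% | 13.5% |
| 1.00% | 85.1% | 14.9% |

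Setting (1 − p)^16 = 0.90 gives p = 1 − 0.90^(1/16) = 0.656%. The bound fails from there up to 1%, which is roughly the top third of the range it claims to cover. At 1% the shortfall is 90 − 85.1 = 4.9 percentage points.

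**Could other inputs give the stated figure?**

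- *Poisson approximation:* exp(−0.16) = 85.2% at 1%, so no change.
- *Fewer recipients:* 0.99^n > 0.90 needs n < ln 0.90 / ln 0.99 = 10.48, so n ≤ 10 (0.99^10 = 90.4%; 0.99^11 = 89.5%). With n = 10 the chance of rule 1 being met at 10% is 1 − 0.90^10 = 65.1%, which breaks the stated 80%.
- *A two-event trigger:* 98.9% not met at 1%, but only 48.5% met at 10%, and it contradicts Table 17.
- *Counting infants or placebo recipients as further units at risk:* this raises n and lowers the chance of not being met, so the gap widens.

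**The case against.** The arithmetic is hard to dispute; the objections go to weight and scope.

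1. *Nothing depends on the sentence.* It illustrates the rules. Rules 1a-1c are assessed continuously by the investigator whatever the number enrolled, and no threshold, sample size or analysis uses the 90% figure. This stands, and it is why the point is minor.
2. *Subject protection is not weakened.* The error understates the chance of a hold at a low event rate. The bound that bears on detecting harm, more than 80% at rates above 10%, is correct. A hold also leads to review and possible restart. This stands too.
3. *The range is narrow, and 85.1% is the value at the endpoint.* That is true, but the statement fails throughout 0.66% to 1%, and the section's other bounds all hold at their endpoints.
4. *The 16-recipient binomial simplifies how rule 1 operates.* Table 17 is not limited to active recipients and counts fetal and infant events. So the corrected figure is not the real-life hold probability either. This is fair, but the protocol chose this basis, and the clause is wrong on that basis.
5. *The figure of 16 may not describe the first planned IDMC meeting.* Section 8.2.3.3.3 places that meeting at 75 mothers dosed, about 50 of them active under 1:1:1 allocation. Sixteen matches the active share of about 24 delivered pairs (24 × 2/3), the number in Section 9.5.1.1. With 50 active recipients the chance of a rule 1 criterion not being met at 1% would be 0.99^50 = 60.5%. This is a separate question. It does not rescue the clause, which is explicitly conditional on 16, but it means that correcting the clause does not settle the whole section.

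**Conclusion.** The concern holds. On the protocol's own inputs, 16 active recipients and a one-event trigger, each of rules 1a-1c has an 85.1% chance of not being met at a true rate of 1%. The claim of more than 90% is correct only below about 0.66%. The chance of a given rule being met at 1% is 14.9%, about 5 percentage points above what the text implies.

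The result assumes independent events with a common rate among the 16 recipients, the same model that reproduces the other three bounds. It needs no figure from outside the protocol. Figure 5 is not visible in the copy reviewed, so its curve may already be right; if so, it disagrees with the sentence that interprets it. Severity is minor: a stated operating characteristic of the safety rules is wrong, with no effect on the rules, the sample size or any analysis.

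**What to change.** Change the one clause in Section 8.2.3.4 in either of two ways:

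- keep the rate and lower the probability: more than 85% chance of not being met for a true incidence rate below 1%; or
- keep the probability and lower the rate: more than 90% chance of not being met for a true incidence rate below 0.65% (0.9935^16 = 90.1%).

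Then check that the sentence agrees with the curve in Figure 5. While the section is open, it would be sensible to confirm that 16 active recipients is the intended basis for the first planned IDMC meeting, given the 75 dosed mothers in Section 8.2.3.3.3.

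The cost is a text correction. The holding rules, sample size and analyses stay as they are.

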| | | - | - | RTI hospitalization | Collect (if possible) from any subject hospitalized with a RTI (or soon after release, as long as symptoms are ongoing). Collection of a nasal swab for sponsor testing is additional to and DOES NOT REPLACE any specimen collection (per local standard of care) for testing by the local laboratory to establish a fast and accurate diagnosis for the hospitalisation. In the case of hospitalization, local testing for RSV infection should be performed if feasible. If other specimens are collected and tested locally as per local standard of care, results will be recorded in the eCRF. However, only the sponsor laboratory results will be used when applying the case definitions for data analysis in Section 8.4.7. Thus, where mandated by the protocol, every effort should be made to obtain samples that can be analyzed by the sponsor (or sponsor-designated) laboratory. |

*Only from infant subjects in the sample collection subcohort for the visit. Each infant is assigned to a single subcohort.

CONFIDENTIAL209544 (RSV MAT-004)
Protocol Amendment 3 Final**8.1.2. Laboratory assays**

Assays performed to evaluate immune response / the presence of RSV infection are listed below.

Table 13 Antibody determination

| System | Component | Method | Laboratory |
|--------|--|--------|---|
| SERUM | RSV-A NAb (RSV-A Neutralizing Antibody) | NEUT | GSK Biologicals** or GSK designated lab |
| SERUM | RSV-B NAb (RSV-B Neutralizing Antibody) | NEUT | GSK Biologicals** or GSK designated lab |
| SERUM | Respiratory Syncytial Virus Pref3 Ab.IgG (RSVPreF3 IgG antibody concentration) | ELISA | GSK Biologicals** or GSK designated lab |

ELISA = enzyme-linked immunosorbent assay; **NEUT** = Neutralization; ** GSK Biologicals laboratory refers to the Clinical Laboratory Sciences (CLS) facilities in Rixensart, Belgium, Marburg, Germany and Wavre, Belgium.

Table 14 Molecular Biology

| System | Component* | Method | Unit | Laboratory |
|---------------------|-----------------------------------|--------|-----------|---|
| NASMUC (Nasal swab) | Respiratory Syncytial Virus A RNA | QRTPCR | Copies/mL | GSK Biologicals or GSK designated lab** |
| NASMUC (Nasal swab) | Respiratory Syncytial Virus B RNA | QRTPCR | Copies/mL | GSK Biologicals or GSK designated lab** |

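### Section 8.2.3.4 sizes the enhanced-disease comparison at one-sided 5% but reads it with one-sided 2.5% limits, calls failure to exclude 80% equivalence, and does not say which infants are counted

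*Protocol*

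**What the plan says.** Section 8.2.3.4 of the protocol asks whether the study could show that the progression rate "is lower than the 80% rate seen in the historical formalin-inactivated vaccine". For this, "the accrual of at least 5 cases of RSV infection among infants will be needed". The error rate and the alternative are fixed in one sentence: "With a one-sided 5% type one error rate and assumption of a 10% rate of infection progressing to severe disease or hospitalization". The claim attached to them is that "5 infections can provide at least 90% statistical power to demonstrate the progression rate" is below 80%.

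The text introducing Table 20 then says how to read a result: "Where the upper limit of the 95% confidence interval is above 80%, this suggests a rate of severe disease that is equivalent". The comparator in that sentence is the formalin-inactivated vaccine used in the past. A limit below 80% is read as the current vaccine not being equivalent to it. Table 20 lists seven examples with 5 or 10 infected infants. Neither the text nor the column headings name a treatment group.

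**The concern.** Three things do not fit together.

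- **Sidedness.** The test is one-sided at 5%, but the limits used to read it are labelled only as 95%. If they are the upper ends of two-sided intervals, the result is judged at half the stated error rate, and the same data can pass one criterion and fail the other.
- **Interpretation.** An upper limit above 80% is a failure to reject. It does not show that the rate is near 80%. With very few cases it will occur often for a vaccine whose progression rate is far below 80%.
- **Population.** By Table 6, one third of infants are in the control group. A comparison with a historical vaccine has meaning only in infants of vaccine recipients. Pooling placebo cases would pull the rate down, which is the falsely reassuring direction.

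Sections 4.2.3 and 8.2.3.4 both say that data on enhanced disease are expected before larger numbers of pregnant women are vaccinated. What this comparison can be said to show therefore matters.

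**Working it through.** **Inputs from Section 8.2.3.4:** null rate 80%, assumed rate 10%, one-sided 5%, 5 or 10 cases, and the seven limits in Table 20. X is the number of cases that progress, taken as binomial.

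**1. The plan's own power.** With 5 cases:
- P(X ≤ 1 | 80%) = 0.2⁵ + 5(0.8)(0.2⁴) = 0.0003 + 0.0064 = 0.0067.
- P(X ≤ 2 | 80%) = 0.0579, above 5%, so the rule is to exclude 80% if X ≤ 1.
- Power at 10% = 0.9⁵ + 5(0.1)(0.9⁴) = 0.5905 + 0.3281 = 91.9%.

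The stated power of at least 90% is reproduced. Since 0.0067 is also below 2.5%, the 5-case rule is the same at both levels.

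**2. The limits in Table 20.** The Clopper-Pearson upper limit is the (1 − a) quantile of Beta(x + 1, n − x). Two-sided 95% uses a = 0.025; a one-sided 5% test corresponds to a = 0.05.

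| Cases | Severe | Printed % | a = 0.025 | a = 0.05 | P(X ≤ x) at 80% |
|---|---|---|---|---|---|
| 5 | 1 | 71.6 | 71.6 | 65.7 | 0.0067 |
| 5 | 2 | 85.3 | 85.3 | 81.1 | 0.0579 |
| 10 | 1 | 45 | 44.5 | 39.4 | <0.0001 |
| 10 | 2 | 56 | 55.6 | 50.7 | 0.0001 |
| 10 | 3 | 65.2 | 65.2 | 60.7 | 0.0009 |
| 10 | 4 | 73.8 | 73.8 | 69.7 | 0.0064 |
| 10 | 5 | 81.3 | 81.3 | 77.8 | 0.0328 |

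All seven printed limits are the a = 0.025 values, two of them rounded to whole percents. Wilson, Agresti-Coull, Jeffreys and Wald limits do not reproduce the table. One row changes side of 80%: at 5 of 10 the stated test excludes 80% (p = 0.033) and the printed limit does not. From 5 to 12 cases the two levels give different rules only at 7 and 10.

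**3. Smallest case number giving at least 90% power.**
- At 5%, 4 cases, rule X ≤ 1: error 0.2⁴ + 4(0.8)(0.2³) = 0.0272; power 0.9⁴ + 4(0.1)(0.9³) = 94.8%. Two or three cases give 81.0% and 72.9%.
- At 2.5%, 4 cases allow only X = 0, with power 0.9⁴ = 65.6%. Five cases give 91.9%.

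So the figure of 5 fits 2.5%; at 5% the figure is 4.

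**4. How often the equivalence label would appear.** With 5 cases it appears when X ≥ 2. The probability is 8% at a true rate of 10%, 26% at 20%, 66% at 40% and 81% at 50%. In Table 20 itself the label falls on observed rates of 40% (2 of 5) and 50% (5 of 10).

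**5. Possible dilution.** Assume vaccine-group progression of 80%, placebo progression of 10% to 20%, and two thirds of cases in the vaccine groups; the placebo rates and the case share are not in the protocol. The pooled rate is (2/3)(80%) + (1/3)(10%) = 56.7%, or (2/3)(80%) + (1/3)(20%) = 60%. The chance of wrongly excluding 80% with 5 cases, P(X ≤ 1), rises from 0.7% to 11.5% or 8.7%. With 10 cases and the printed limits, P(X ≤ 4), it rises from 0.6% to 23% or 17%.

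**The case against.** The comparison is not a decision rule. It sits under risk assessment, its rows are examples, and Section 9.1 calls all analyses descriptive. The holding rules are in Tables 17 and 18, and none refers to Table 20. This stands, and it limits the severity.

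The sidedness mismatch is small. The 5-case power is correct, planning for 5 when 4 would do is conservative, and the printed limits are the stricter ones, so they cannot clear a vaccine that the stated test would not. That stands too. It does not make the two statements agree, and one of the sponsor's own rows falls between them.

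The probabilities in step 4 are ordinary non-rejection probabilities for a 5-case test, and rewording will not lower them. True, but the fault lies in what the protocol says the outcome means.

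A reader might infer that placebo infants are counted towards the 5 cases. The protocol does not say so. The conclusion is worded about the current vaccine, Sections 9.4.1.1 and 9.4.4.1 tabulate RSV illness by group, and under Section 8.2.3.3.3 the IDMC sees unblinded data. What remains is an ambiguity: none of these defines the cases for the 80% comparison, while elsewhere Section 8.2.3.4 does specify active vaccine recipients.

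A reader might also infer from Table 12, where "only the sponsor laboratory results will be used when applying the case definitions for data analysis", that the most severe cases are lost. The documents do not support that. Confirmation by a single assay is a deliberate choice. Section 8.4.6 asks for a sponsor swab at every hospitalisation for respiratory illness, and those hospitalisations are reported as SAEs within 24 hours and reach the IDMC.

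**Conclusion.** The point holds as a wording and consistency fault that should be fixed. The stated error rate and the Table 20 limits differ by a factor of two; among the printed rows this reverses only 5 of 10, and it leaves the 5-case rule and its 91.9% power unchanged. The minimum of 5 cases is right only at one-sided 2.5%. Reading a limit above 80% as equivalence is wrong at any level. These results need only the protocol's own inputs and the binomial model.

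The missing restriction to vaccine-group infants is an ambiguity, not a stated pooling rule. Its size, about 9% to 12% instead of 0.7% with 5 cases, rests on the assumed placebo rates and case share. It would not be right to conclude that the trial has a faulty stopping rule or that its enhanced-disease power claim is wrong.

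**What to change.** In Section 8.2.3.4:

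1. State one-sided 2.5%, which matches Table 20 and the 5-case figure. Power stays at 91.9%. The alternative is to keep 5%, reprint Table 20 with one-sided 95% limits and restate the minimum as 4 cases. Either is coherent; the first changes less.
2. For a limit above 80%, say that 80% is not excluded and the result is inconclusive. For a limit below 80%, say that the rate is lower than 80%.
3. State that the cases are those in infants of RSVPreF3 recipients, with placebo infants shown alongside.

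No new data are needed. The one practical cost is in item 3: if two thirds of cases arise in the vaccine groups, 5 qualifying cases correspond to about 5 ÷ (2/3) = 7.5 cases overall, so the comparison may become available later than a pooled count would suggest.
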